6.4 Sample Size

Previous studies (detailed in Section 2.2, Table 1) indicate that approximately 40% of patients will experience severe OM with radiation and concurrent chemotherapy. The hypothesis in this trial is that the addition of LLLT to this treatment regimen will decrease the rate of severe acute OM to 20%. A sample size of 45 yields 90% power to detect a difference of 0.20 using an exact one-sided binomial test with a Type I error of 0.05. A total of 50 patients are required to ensure that there are at least 45 compliant with the treatment schedule. Subjects who miss >20% of planned LLLT treatments will be considered non-compliant with the protocol. All patients should be enrolled in 12 months after the trial opens. We plan to enroll 25 patients at our institution. The same protocol will be opened separately at the University of Pittsburgh Medical Center (UPMC), where an additional 25 patients will be enrolled. A Data Use Agreement will allow combination of the data for a total of 50 patients to be analyzed.

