6.0 Statistical Considerations

6.1 Primary Endpoints:

- The incidence of severe (WHO grade 3-4) oral mucositis in patients treated to a cumulative radiation dose of at least 5000 cGy.
- The incidence of severe (CTCAE v. 4.0 grade 3-5) oral mucositis in patients treated to a cumulative radiation dose of at least 5000 cGy.

6.2 Secondary Endpoints:

- Time to onset of severe (CTCAE v. 4.0 grade 3-4) oral mucositis following the initiation of radiotherapy.
- Mean cumulative radiation dose at time of onset of severe (CTCAE v. 4.0 grade 3-4) oral mucositis.
- Duration of oral mucositis.
- The incidence of pain.
- The incidence of dysphagia (CTCAE v. 4.0 and via diet assessment).
- The incidence of xerostomia (CTCAE v. 4.0).
- The incidence of dysgeusia (CTCAE v. 4.0).
- The incidence of trismus (Measurement of interincisal distance).
- The incidence of radiodermatitis (CTCAE v. 4.0).
- Evaluation of OM-related QOL (via FACT-H&N score).
- Incidence of any grade oral mucositis in patients treated to a cumulative radiation dose of at least 5000 cGy.

6.3 Exploratory Endpoints:

- Proportion of patients with severe (CTCAE v. 4.0 grade 3-4) oral mucositis by 5000 and 7000 cGy.
- Proportion of patients with severe (CTCAE v. 4.0 grade 3-4) oral mucositis by schedule of chemotherapy given (weekly versus Q 3 weeks).
- Time to reach planned dose of radiation therapy.
- Amount of narcotic analgesia use during treatment.
- Assessments of breaks in treatment defined as one of the following:
 - Missing at least 1 chemotherapy treatment;
 - Dose reduction in planned cisplatin administration; OR
 - 3 consecutive days of no RT secondary to mucositis. ~
- Proportion of patients who require feeding tube placement during treatment (excluding patients who received a prophylactic feeding tube prior to the initiation of therapy).
- Percent change in body weight during the course of treatment.

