6.5 Analysis

Primary endpoint

If 12 or fewer out of the 45 evaluable severe OM events occur (WHO grade 3-4 or CTCAE v. 4.0 grade 3-5 oral mucositis), we will reject the null hypothesis that the occurrence of severe OM is 0.4 with the addition of LLLT therapy. Point and 90% confidence intervals (using Wilson's method) will also be estimated to describe the primary endpoint.

Secondary endpoints

Descriptive statistics (point and exact 90% confidence interval estimates from the resultant Kaplan-Meier curve) will be generated for the time-to-severe OM and duration of severe OM endpoints. Point and 90% confidence intervals (using Wilson's method) will also be estimated to describe the binary endpoints. Continuous endpoints will be described by 90% confidence intervals using the t-distribution.

Exploratory endpoints

Similar descriptive analyses as described in the above paragraph will be used for the binary, time-to-event and continuous endpoints.

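### Section 6.5 gives one rejection cutoff, 12 of 45, that is correct only for 45 to 47 evaluable patients, while Section 6.4 leaves the evaluable number open

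*Combined protocol and SAP*

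**What the plan says.** Section 6.4 (Sample Size) sets the design: "A sample size of 45 yields 90% power to detect a difference of 0.20 using an exact one-sided binomial test with a Type I error". The level is set at 0.05, and the rates are 40% under the null and 20% under the alternative. On enrolment it says "A total of 50 patients are required to ensure that there are at least 45 compliant with the treatment schedule", and it defines the loss it has in mind: "Subjects who miss >20% of planned LLLT treatments will be considered non-compliant with the protocol". No expected rate of non-compliance is given. The section ends by saying that data from the two centres will be combined so that 50 patients are analysed.

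Section 6.5 (Analysis) turns the design into one rule: "If 12 or fewer out of the 45 evaluable severe OM events occur", on either grading scale, then "we will reject the null hypothesis that the occurrence of severe OM is 0.4 with the addition of LLLT therapy". No other evaluable number is covered, and evaluable is not defined.

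Section 6.1 restricts both primary endpoints by radiation dose. The first reads "The incidence of severe (WHO grade 3-4) oral mucositis in patients treated to a cumulative radiation dose of at least 5000 cGy"; the CTCAE version carries the same condition. The documents give no rule for replacing patients.

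**The concern.** The rule in 6.5 works for exactly one denominator, but the plan itself points to others: at least 45, or all 50. An exact binomial cutoff depends on the denominator. If 12 is carried over to fewer than 45 patients, the test is too lenient for the stated 0.05. If it is carried over to 48 or more, the test is stricter than it need be and loses power. If the cutoff is worked out only after the count is known, the primary decision rule looks as if it was chosen after the data, in an open-label single-arm trial whose conclusion rests on one event count.

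Two results show what is at stake. Twelve events in 44 patients would be called a success if 12 were kept, although the exact one-sided p-value is 0.056. Thirteen events in 50 would be called a failure, although the exact p-value is 0.028.

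**Working it through.** **Inputs.** Null rate 0.40 (6.4, 6.5); alternative 0.20 (6.4); exact one-sided binomial test at 0.05 (6.4); cutoff 12 at N = 45 (6.5); 50 enrolled for at least 45 compliant (6.4). The loss rate is not in the documents. I take 10% as an assumption, because 45/0.90 = 50, and show 5% to 20%.

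**Step 1: reproduce the plan's figure.** With X ~ Bin(45, p):
- alpha = P(X ≤ 12 | p = 0.40) = 0.0446
- power = P(X ≤ 12 | p = 0.20) = 0.9005
- the next cutoff, 13, has alpha 0.0836, so 12 is the largest allowed.

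The stated 90% power and the cutoff are both correct at N = 45.

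**Step 2: cutoff at other N.** For each N, take the largest c with P(X ≤ c | N, 0.40) ≤ 0.05; power is P(X ≤ c | N, 0.20). The last two columns keep c = 12 regardless of N.

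| N | correct c | alpha | power | alpha if 12 kept | power if 12 kept |
|---|---|---|---|---|---|
| 40 | 10 | 0.035 | 0.839 | 0.129 | 0.957 |
| 41 | 10 | 0.027 | 0.818 | 0.105 | 0.948 |
| 42 | 11 | 0.045 | 0.882 | 0.086 | 0.938 |
| 43 | 11 | 0.035 | 0.864 | 0.070 | 0.927 |
| 44 | 11 | 0.028 | 0.846 | 0.056 | 0.914 |
| 45 | 12 | 0.045 | 0.901 | 0.045 | 0.901 |
| 46 | 12 | 0.035 | 0.886 | 0.035 | 0.886 |
| 47 | 12 | 0.028 | 0.869 | 0.028 | 0.869 |
| 48 | 13 | 0.044 | 0.916 | 0.022 | 0.852 |
| 49 | 13 | 0.035 | 0.903 | 0.017 | 0.834 |
| 50 | 13 | 0.028 | 0.889 | 0.013 | 0.814 |

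Below 40, the correct cutoff is 9 for N = 36 to 38 and 10 for N = 39. So 12 is right only for N = 45 to 47. With correct cutoffs, power lies between 0.82 and 0.92 for N = 40 to 50.

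**Step 3: how likely is another N?** If each of 50 patients is lost independently with probability d, the evaluable number is Bin(50, 1 − d).

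| loss d | P(N ≥ 45) |
|---|---|
| 5% | 0.96 |
| 8% | 0.79 |
| 10% | 0.62 |
| 12% | 0.44 |
| 15% | 0.22 |
| 20% | 0.05 |

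At 10% loss, N falls in 45 to 47 with probability 0.50: P(N ≥ 45) is 0.616 and P(N ≥ 48) is 0.112, and 0.616 − 0.112 = 0.504. N is below 45 with probability 1 − 0.616 = 0.384.

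**Step 4: average power.** Weighting the power at each N, with its correct cutoff, by the chance of that N gives 0.894, 0.877, 0.858 and 0.836 at 5%, 10%, 15% and 20% loss.

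**The case against.** The strongest reply is that nothing in the plan is miscalculated. Power is normally quoted at the design N, the quoted power is right, and 45/(1 − 0.10) = 50 is the usual inflation for loss. Section 6.4 also fixes the test, the null rate and the alpha, so a statistician can derive the cutoff at any N without a new decision. All of this stands, and it makes the point one of completeness and wording.

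It does not remove the gap. The rule in 6.5 is written as a fixed count for a fixed denominator, and no sentence says that it is to be re-derived. Someone applying it literally at 44 or at 50 would follow the text and depart from the design.

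Three stronger readings are tempting and are not supported:

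- **That the trial is underpowered or the sample size is wrong.** The 90% holds at 45, and with correct cutoffs average power is still about 88% at 10% loss. The dips at 46 and 47 are the ordinary sawtooth of an exact test.
- **That the 62% is a property of the plan.** It rests on a loss rate that the documents do not state; at 5% loss it is 96%.
- **That the margin of five must also absorb further losses, from patients below 5000 cGy and from withdrawals.** Section 6.1 does condition on dose, and Section 3.3 lists several reasons for ending participation. But the inclusion criteria already require a planned dose of 5000 to 7000 cGy, and LLLT runs alongside radiotherapy (4.3), so these patients may largely be the same ones who miss LLLT sessions. The documents give no figure for any additional loss.

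It is also fair to say that if all 50 are analysed, the chance of reaching 45 compliant no longer governs the test. But the printed cutoff is then wrong for the denominator actually used, and power drops to 0.81.

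**Conclusion.** The point holds as a gap in the primary decision rule. The single cutoff of 12 is correct for 45 to 47 evaluable patients and for no other number. Kept elsewhere, it exceeds the stated 0.05 at 44 or fewer (0.056 at 44, 0.070 at 43, 0.086 at 42). It also gives up about 8 points of power at 50 (0.81 against 0.89). These figures rest only on the plan's own rates, test and alpha.

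How often this would matter depends on the assumed loss. At 10%, the evaluable number lies outside 45 to 47 about half the time, and the chance of at least 45 is 0.62. The word *ensure* in 6.4 is therefore too strong, but that is a matter of wording. The design at 45 is sound.

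**What to change.** **Section 6.5.** State that the cutoff is the largest c with P(X ≤ c | N, 0.40) ≤ 0.05 at the realised evaluable N, and print it:

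| evaluable N | reject if events ≤ |
|---|---|
| 36–38 | 9 |
| 39–41 | 10 |
| 42–44 | 11 |
| 45–47 | 12 |
| 48–50 | 13 |

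The general rule covers any smaller number.

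**Section 6.4.** Replace the assurance of 45 with an expected 45 if total loss is 10%. Keep 90% as the power at N = 45, and add that power is about 82% to 92% for 40 to 50 evaluable patients, about 88% on average at 10% loss.

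**Both sections.** Define evaluable, and reconcile 45 evaluable in 6.5 with 50 analysed in 6.4, so that the denominator of the primary test is fixed in advance.

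The cost is a few lines and one small table, with no added enrolment. The stated power becomes slightly less favourable.

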6.5 Analysis

Primary endpoint

If 12 or fewer out of the 45 evaluable severe OM events occur (WHO grade 3-4 or CTCAE v. 4.0 grade 3-5 oral mucositis), we will reject the null hypothesis that the occurrence of severe OM is 0.4 with the addition of LLLT therapy. Point and 90% confidence intervals (using Wilson's method) will also be estimated to describe the primary endpoint.

Secondary endpoints

Descriptive statistics (point and exact 90% confidence interval estimates from the resultant Kaplan-Meier curve) will be generated for the time-to-severe OM and duration of severe OM endpoints. Point and 90% confidence intervals (using Wilson's method) will also be estimated to describe the binary endpoints. Continuous endpoints will be described by 90% confidence intervals using the t-distribution.

Exploratory endpoints

Similar descriptive analyses as described in the above paragraph will be used for the binary, time-to-event and continuous endpoints.

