3.0 SelectionandWithdrawalofSubjects

3.1 StudyDesign

This is a phase II prospective, single-arm, open label trial testing the efficacy of LLLT in prevention of oral mucositis for HNC patients treated with chemoradiotherapy. Primary endpoints are the incidence of severe (assessed separately as CTCAE v. 4.0 grade 3-5 or WHO grade 3-4) OM in patients receiving a cumulative radiation dose of at least 5000 cGy. Secondary endpoints include the time onset to severe OM, mean cumulative radiation dose at the time of OM, duration of OM, the incidence of pain, dysphagia, xerostomia, dysgeusia, trismus, radiodermatitis, and QOL.

All toxicities will be graded by NCI CTCAE v. 4.0. In addition, oral mucositis will also be graded by WHO mucositis grading scale. Dysphagia will also be graded by a dietary assessment. Trismus will be assessed by measurements of the interincisal distance. QOL will be measured by the FACT-H&N assessment.

Previous studies (detailed in Section 2.2, Table 1) indicate that approximately 40% of patients will experience severe OM with radiation and concurrent chemotherapy. The hypothesis in this trial is that the addition of LLLT to this treatment regimen will decrease the rate of severe acute OM to 20%. We plan to enroll 25 patients at our institution in 12 months after the trial opens. The same protocol will be opened separately at the University of Pittsburgh Medical Center (UPMC), where an additional 25 patients will be enrolled. A Data Use Agreement will allow combination of the data for a total of 50 patients to be analyzed.

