5.2 Follow-up Assessments

During each assessment, the following toxicities will be assessed: pain, OM, dysphagia, xerostomia, dysgeusia, dermatitis, trismus, and QOL.

Mouth pain and throat pain severity will be assessed weekly using a standard 0-10 scale. A record of the amount of analgesic medications required will be required at each visit.

A diet assessment will be performed at weekly on-treatment assessments as follows:

DietAssessment		

Diet1: What has the subject been able to eat within the past 24 hours (mark only one)
 
 Solids  Liquids  Nothing by Mouth
 
If Solids is marked above, proceed to next section. If Liquids or Nothing by Mouth is marked about continue to "Diet 2".
	
Diet2: If the subject has been unable to eat Solid food, mark all the reason(s) why (mark all that apply)
 
 Nausea/Vomiting  Loss of appetite  Throat discomfort  Difficulty Swallowing  Other _____
 
If Oraldiscomfort is marked above, proceed to the next section. If Oraldiscomfort is NOT marked above, proceed to "Diet 3".
	
Diet3: Based solely on how the mouth feels, what does the subject feel (s)he could try to eat if (s)he did not have to swallow (mark only one)
 
 Solids  Liquids  Nothing by Mouth

OM will be assessed using the NCI CTCAE version 4.0 [25] as follows:

Adverse Event	Grade				
	1	2	3	4	5
Oral Mucositis	Asymptomatic or mild symptoms; intervention not indicated	Moderate pain; not interfering with oral intake; modified diet indicated	Severe pain; interfering with oral intake	Life-threatening consequences; urgent intervention indicated	Death

OM will also be assessed using the World Health Organization (WHO) grading scale [26]:

WHO Oral Mucositis Grade	
Grade 0 (None)	None
Grade 1 (Mild)	Oral soreness/erythema
Grade 2 (Moderate)	Oral soreness/erythema, ulcers, can tolerate solid foods
Grade 3 (Severe)	Oral soreness/erythema, ulcers, liquid diet only
Grade 4 (Life-threatening)	Oral alimentation is not possible

Patient-reported OM outcomes will be assessed using the Oral Mucositis Daily Questionnaire (OMDQ) [27]

OralMucositisDailyQuestionnaire

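### Two primary endpoints (WHO and CTCAE) share one cutoff and one 0.05-level test, with no rule for the overall conclusion if one scale passes and the other does not

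*Combined protocol and SAP*

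**What the plan says.** Section 3.1 introduces the primary endpoints in the plural: severe oral mucositis is "assessed separately as CTCAE v. 4.0 grade 3-5 or WHO grade 3-4". Section 6.1 lists them as two items, one on WHO grade 3-4 and the other as "The incidence of severe (CTCAE v. 4.0 grade 3-5) oral mucositis in patients treated to a cumulative radiation dose of at least 5000 cGy".

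Section 6.4 has a single calculation: 45 patients, 40% against 20%, 90% power, "using an exact one-sided binomial test with a Type I error of 0.05". It does not give the rates by scale.

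Section 6.5 has a single rule: "If 12 or fewer out of the 45 evaluable severe OM events occur (WHO grade 3-4 or CTCAE v. 4.0 grade 3-5 oral mucositis"), the null rate of 0.4 is rejected. It adds that an estimate and a 90% Wilson interval "will also be estimated to describe the primary endpoint", in the singular.

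No section names a deciding scale, requires both, sets an order of testing or divides the alpha. Section 3.1 grades all toxicities by CTCAE and then says: "In addition, oral mucositis will also be graded by WHO mucositis grading scale". That describes data collection and does not make either scale decisive. The calendar in 11.10 schedules both scales at the same visits, so every patient will contribute to two tallies.

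**The concern.** The definitions in Section 5.2 let the two tallies differ. WHO grade 3 depends on ulcers and a liquid-only diet. CTCAE grade 3 depends on severe pain that interferes with intake. A patient with ulcers and severe pain that limits intake, who can still manage solids, is CTCAE 3 and WHO 2.

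The reverse (WHO 3, CTCAE 2) is less natural, because CTCAE grade 2 reads "Moderate pain; not interfering with oral intake; modified diet indicated". It is not excluded, since that grade allows a modified diet. The documents therefore do not settle whether disagreement runs one way or both ways.

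If the tallies fall on opposite sides of the cutoff, the plan gives no overall conclusion. The choice between 'either suffices' and 'both must pass' would then be made with the results in view. The 0.05 error rate and 90% power in Section 6.4 describe one test, so they do not automatically carry over to whichever combined claim is chosen.

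**Working it through.** **Inputs.** n = 45, null 0.40, alternative 0.20, one-sided 0.05 (6.4); cutoff 12 (6.5). The documents give no agreement between scales and no rate for each scale. Both are assumptions below. Agreement is the within-patient correlation φ of the two yes/no gradings.

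**Step 1: the plan's own figures, one scale.**
- P(X ≤ 12 | 45, 0.40) = 0.0446
- P(X ≤ 13 | 45, 0.40) = 0.0836
- P(X ≤ 12 | 45, 0.20) = 0.9005

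The cutoff, alpha and power all reproduce for one scale.

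**Step 2: how close the call can be.** 12/45 rejects (one-sided p = 0.0446; 90% Wilson interval 0.1738 to 0.3860, which excludes 0.40). 13/45 does not (p = 0.0836; 0.1923 to 0.4095, which includes it). At that boundary, one discordant patient puts the two scales on opposite sides.

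**Step 3: two scales with equal rate p.** The probability that a patient is severe on both is p11 = p² + φp(1 − p). At φ = 0.8 and p = 0.40, p11 = 0.16 + 0.8 × 0.24 = 0.352. That leaves 0.40 − 0.352 = 0.048 severe on each scale alone and 0.552 severe on neither. Adding up 45 such patients gives the exact joint distribution of the two counts and hence P(both ≤ 12). Then:
- P(either ≤ 12) = 2 × P(one scale ≤ 12) − P(both ≤ 12)
- P(exactly one ≤ 12) = 2 × [P(one scale ≤ 12) − P(both ≤ 12)]

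At φ = 0.8 and p = 0.40, P(both) = 0.0220, so either = 2 × 0.04463 − 0.0220 = 0.0673 and exactly one = 2 × (0.04463 − 0.0220) = 0.0453.

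| φ (assumed) | Type I error, either suffices (both 40%) | Power, both must pass (both 20%) | Exactly one passes (both 20%) | Exactly one passes (both 40%) |
|---|---|---|---|---|
| 0 | 8.7% | 81.1% | 17.9% | 8.5% |
| 0.5 | 7.9% | 83.5% | 13.2% | 6.9% |
| 0.8 | 6.7% | 85.9% | 8.3% | 4.5% |
| 0.9 | 6.0% | 87.3% | 5.6% | 3.1% |
| 1 | 4.46% | 90.05% | 0% | 0% |

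The φ = 0 row is only a bound. Two gradings of the same mouth will not be independent.

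**Step 4: unequal rates.** Suppose discordance is one-way, so that every patient severe on one scale is also severe on the other.
- At 40%/45%, 'either suffices' reduces to the lower-rate scale, and type I error stays at 4.46%.
- At 20%/25%, 'both must pass' reduces to the higher-rate scale: P(X ≤ 12 | 45, 0.25) = 0.6748. Exactly one passes in 0.9005 − 0.6748 = 0.2257 of trials.

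With two-way discordance at 40%/42%, 'either suffices' gives 0.0625, 0.0542 and 0.0493 at φ = 0.5, 0.8 and 0.9.

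**The case against.** The strongest defence is that Section 3.1 already answers the question. The endpoints are assessed separately, so each is compared with the same null and cutoff, and each keeps 4.46% and 90.05% if its own rates are 40% and 20%. Each endpoint then has a definite result. This is a single-arm phase II trial, and the documents attach no interim gate or treatment decision to one overall verdict. At a correlation of 0.8 the scales agree in more than 90% of trials.

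Much of this stands, and it limits the point in three ways.

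- A reader might infer that a patient counts as an event if severe on either scale, because Section 6.5 joins the scales by 'or'. The separate assessment in 3.1 and the two items in 6.1 argue against such a composite, so it is not treated here as a live reading.
- A reader might infer that type I error must be inflated. It is inflated only if either scale suffices and discordance runs both ways at similar rates.
- A reader might put the whole 22.6% at 20%/25% down to the missing rule. Most of it arises because the higher-rate scale has only 67% power of its own.

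The defence does not supply the missing rule. Separate assessment does not say what the trial concludes from one pass and one failure, and 6.5 still announces one rejection of one null for one primary endpoint.

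**Conclusion.** The concern holds in a limited form. The cutoff, alpha and power are correct for one scale. What is missing is the rule for the overall conclusion when two separately assessed primary endpoints differ. Three readings remain: either suffices, both must pass, or two separate conclusions.

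Under equal rates and correlations of 0.5 to 0.9, the cost is type I error of 7.9% to 6.0% under the first reading, or power of 83% to 87% instead of 90% under the second. The third keeps the stated figures per endpoint but supports no single claim when the scales differ. The correlations and equal rates are assumptions.

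It would go too far to say that the primary result is undetermined altogether. Each scale has a definite tally and a usable cutoff, and the gap bites only when the two fall on opposite sides of it. It should be fixed, because it concerns the trial's only formal efficacy test and the remedy is short.

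**What to change.** Before outcome data are reviewed, amend 3.1, 6.1, 6.2 and 6.5. Name one scale as the single tested primary endpoint, remove 'or' from the rule, and move the other scale to 6.2 as a descriptive endpoint with a 90% Wilson interval. Possible wording for 6.5:

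> *Among evaluable patients who received 5000 cGy or more, the null hypothesis of a 0.40 rate of severe oral mucositis on [named scale] is rejected if no more than 12 of 45 have the event (exact one-sided 0.05 test; the exact cutoff is recalculated if the evaluable number is not 45).*

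With 45 evaluable patients and rates of 40% against 20% on that scale, type I error is 4.46% and power 90.05%.

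Either scale can be defended. WHO matches the 40.5% control rate that Table 1 gives for one chemoradiation trial; Table 1 gives no severe rate on CTCAE v4.0. CTCAE matches the severe-mucositis endpoints in 6.2 and 6.3. If WHO is named, 6.2 should state the mismatch with those endpoints.

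If the sponsor keeps both as primary, 6.5 should say one of two things:
- Success requires both, with power restated: about 83% to 87% at correlations of 0.5 to 0.9 if both true rates are 20%, and lower if one rate is higher.
- Each is concluded separately, the 0.05 type I error applies per endpoint only, and no overall success is claimed when they differ.

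**Cost.** Section 9.1 requires a written, reviewed amendment, with IRB approval if scientific quality is significantly affected. It is needed at both centres, because "The same protocol will be opened separately at the University of Pittsburgh Medical Center (UPMC"). No patients or visits are added, since both scales are already collected. If one scale is named, the other can no longer support a primary claim on its own.
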